9.3.2.4 Patient-reported outcomes

The patient reported outcomes (MDADI, UW-QOL and EQ-5D-5L) will be collected as numeric scores at each time point as outlined in Section 5.4. Patients with disease recurrence will be excluded. The changes in these outcomes from baseline to the subsequent time points will be analyzed using generalized estimating equations.

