2.0 STUDY OBJECTIVES

2.1 Primary Objectives

2.1.1 To determine the maximally tolerated dose/fractionation (MTD) of HFRT

2.2 Secondary Objectives

2.2.1 To assess physician-reported acute and late toxicities of HFRT

2.2.2 To assess the oncologic outcomes of HFRT

2.2.3 To assess patient-reported QOL of HFRT

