5.3 Follow-up Procedures

Patients will be assessed by a radiation oncologist and/or advanced practice provider at 1 month (+/- 1 week) and 3 months (+/- 2 weeks) from the completion of treatment per Time and Events Table (Section 5.4). More frequent visits are encouraged if the patient requires additional help with recovery and rehabilitation. Restaging PET/CT must be performed between 12-14 weeks from the completion of treatment.

Patients with a clinical complete response (cCR) based on history and physical exam and restaging PET/CT at 12-14 weeks as defined in Section 6.1.1 will undergo routine surveillance. Patients with less than cCR in the primary site will undergo directed biopsy of suspected site(s), and if positive, proceed with salvage transoral robotic surgery

(TORS). Patients with less than cCR in the neck will undergo neck dissection, with the extent of the neck dissection to be determined by surgeon discretion.

Patients with pathologically confirmed viable residual primary disease will be considered to have locoregional failure. Since the viability of residual nodal disease on pathology is often questionable at this time point (12-14 weeks post-treatment), and because adjuvant neck dissection is typically considered part of the original treatment package, residual nodal disease at neck dissection will not be considered a locoregional failure.

Patients will then be seen at 6 and 12 months (+/- 4 weeks) from the completion of treatment per Time and Events Table (Section 5.4). Patients with pathologically confirmed recurrent disease following assessment at these times points will be considered to have locoregional failure/recurrence. Subsequent and intervening follow-up visits will be made per physician preference.

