6.0 MEASUREMENT OF EFFECT

6.1 Antitumor Effect

6.1.1 Definitions

Evaluable for toxicity: All subjects will be evaluable for toxicity from the time of their first treatment with radiotherapy.

Clinical complete response (cCR): Disappearance of all lesions on physical/clinical exam and negative PET/CT (12-14 weeks post-treatment), defined as no focal FDG avidity at the primary site (i.e. may have diffuse avidity consistent with post-radiation inflammation) and no focal FDG avidity above blood pool or liver of treated pathological lymph nodes per the Hopkins criteria (24). There can be no appearance of new lesions.

Locoregional recurrence (LRR): Biopsy-proven viable cancer originating from the primary tumor site (i.e. oropharynx) or a lymph node basin above the clavicles.

Locoregional control (LRC): Freedom from locoregional recurrence

Distant metastasis (DM): Recurrent cancer below the clavicles. Biopsy is strongly recommended but not mandated. If biopsy is not obtained, the initiation of anti-cancer therapy is assumed to indicate metastasis, with the date of scan prompting therapy serving as the date of metastasis.

Progression: locoregional recurrence or distant metastasis

Progression-free survival (PFS): Duration of time from start of treatment to time of progression or death.

Overall survival (OS): Duration of time from start of treatment to time of death.

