9.1.3 Secondary endpoints

- Physician-reported acute and late toxicities
 - Rate of \geq grade 3 acute toxicities during treatment, and at 1 and 3 months after treatment using CTCAE v5.0
 - Rate of \geq grade 3 late toxicities at 6 and 12 months after treatment using CTCAE v5.0
- Oncologic outcomes: LRC, PFS, and OS from start of treatment
- Patient-reported QOL:

- MDADI, UW-QOL, and EQ-5D-5L scores at baseline, 1, 3, 6, and 12 months after treatment
- Feeding tube dependence rate at baseline, 1, 3, 6, and 12 months after treatment

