9.3.2.5 Feeding tube dependence

The prevalence of feeding tube use will be described at each time point as outlined in section 5.4.

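### The quality-of-life analysis excludes patients with recurrence without saying from when, so read literally it discards valid changes from baseline recorded before the recurrence

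*Combined protocol and SAP*

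**What the plan says.** The objective in section 2.2.3 is "To assess patient-reported QOL of HFRT". The endpoints in section 9.1.3 are "MDADI, UW-QOL, and EQ-5D-5L scores at baseline, 1, 3, 6, and 12 months after treatment".

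Section 9.3.2.4 analyses changes from baseline to each later visit with generalized estimating equations (GEE). Its only statement on the analysis set is "Patients with disease recurrence will be excluded". No date, visit or phrase limits this to scores after the recurrence. The objective, the endpoint lists (2.3.2 and 9.1.3), the schedule (5.4) and the instrument descriptions (6.3) do not narrow it either.

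Outcomes are assessed at 12-14 weeks and at 6 and 12 months (5.3, 6.1.3). Section 9.3.2.4 does not define recurrence, but the meaning can be taken from elsewhere:
- Section 6.1.1 has "Progression: locoregional recurrence or distant metastasis", with distant metastasis as "Recurrent cancer below the clavicles".
- Section 5.3 classifies residual disease at 12-14 weeks: "Patients with pathologically confirmed viable residual primary disease will be considered to have locoregional failure", whereas "residual nodal disease at neck dissection will not be considered a locoregional failure".

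**The concern.** The rule selects patients on something that happens after treatment. Someone whose recurrence is found at 12 months has by then given recurrence-free scores at baseline and at 1, 3 and 6 months. Applied as written, the rule drops all of them. The 1-, 3- and 6-month estimates then describe a group that cannot be identified until follow-up ends, and membership depends on the outcome of the regimen under test.

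Keeping the effects of recurrence and its treatment out of the quality-of-life results is a reasonable aim. It requires setting aside only the scores from the recurrence onward. At stake is whether early quality of life on the regimen is reported for the patients who received it or for a subset chosen by later outcome. If patients who later recur already have worse changes from baseline, the early results look slightly too favourable.

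**Working it through.** **Inputs.** Sections 7.5 and 9.2: 24 patients, 20 evaluable at 1 year, 15% attrition, and a stop at a 4th locoregional recurrence. Section 9.1.3: five assessments. Section 1.1: 2-year PFS of 90.5% and 86% in two 60 Gy studies. Section 6.3.2: a 10-point MDADI difference is clinically meaningful. The documents give no standard deviation, power or hypothesis for quality of life.

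**The plan's own figure.** 20 / (1 − 0.15) = 23.5, rounded up to 24. This reproduces, and no stated number is disputed.

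**Values lost per patient.** The analysis uses changes from baseline, so each patient contributes four values (1, 3, 6 and 12 months): 20 × 4 = 80 per instrument. The 12-14 week assessment is treated as the 3-month visit, and the value from the detecting visit is counted as post-recurrence. Valid values lost to the literal rule:

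| Recurrence found at | Lost per patient | Lost if 3 of 20 recur |
|---|---|---|
| 3 months | 1 (1 month) | 3 of 80 (3.8%) |
| 6 months | 2 (1, 3 months) | 6 of 80 (7.5%) |
| 12 months | 3 (1, 3, 6 months) | 9 of 80 (11.3%) |

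Three is illustrative: it is the number of locoregional recurrences that section 7.5 tolerates among 20. That rule does not cap distant metastases.

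**Expected loss at the section 1.1 rates.** Assume a constant hazard h = −ln(S₂)/2 per year, where S₂ is the 2-year PFS and S(t) = exp(−ht).

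- S₂ = 0.905: h = 0.0499; S(0.25) = 0.9876, S(0.5) = 0.9754, S(1) = 0.9513. Event probabilities for 0-3, 3-6 and 6-12 months are 0.0124, 0.0122 and 0.0240. Expected patients excluded: 20 × 0.0487 = 0.97. Chance of at least one: 1 − 0.9513²⁰ = 0.63. Values lost: 20 × (1 × 0.0124 + 2 × 0.0122 + 3 × 0.0240) = 2.2 of 80 (2.7%).
- S₂ = 0.86: h = 0.0754; S(0.25) = 0.9813, S(0.5) = 0.9630, S(1) = 0.9274. Probabilities are 0.0187, 0.0183 and 0.0356. Expected patients excluded: 1.45. Chance of at least one: 0.78. Values lost: 20 × (0.0187 + 2 × 0.0183 + 3 × 0.0356) = 3.2 of 80 (4.1%).

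With all 24 patients contributing, the losses are 2.6 and 3.9 of 96, the same percentages. PFS also counts deaths, so at a given PFS these figures overstate recurrence. Follow-up visits run from the end of treatment; that offset of a few weeks is ignored.

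**Shift in a visit mean.** If k of N patients recur after a visit and their mean change at that visit is d points worse, dropping them moves the mean by (k/N) × d. The documents give no d, so these are assumed:

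- d = 0 to 10, k = 1 to 3 of 20: 0 to 1.5 points.
- d = 10 to 30, k = 1 to 3 of 20: 0.5 to 4.5 points.
- d = 10 to 30 at the section 1.1 rates: 0.0487 × 10 = 0.5 to 0.0726 × 30 = 2.2 points.

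The last line counts every first-year event, so it is nearest the truth at 1 month and too high at 3 and 6 months. At 12 months both rules drop the same values. All results are below 10 MDADI points.

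**The case against.** **The sentence can be read visit by visit.** It follows one about scores at each time point, and someone recurrence-free at 1 month is not, at that visit, a patient with recurrence. This reading is possible but less literal, and nothing else in the documents supports it. A reader should still not infer a deliberate decision to discard early data: what the text shows is a rule without a cut-off. Either reading calls for the same edit.

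**The effect is small.** This stands. Quality of life is one of several secondary endpoints in a 24-patient single-arm phase I trial, with no hypothesis or threshold attached. The expected figures are also soft. In the study with 86% PFS at 2 years, PFS was 85% at 3 years, which suggests early events. That could raise the first-year count and lower the number of values lost per patient.

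**The loss could be overstated.** Counting baseline as a lost outcome would give 2 to 4 of 100 scores per patient, but baseline enters only through the change. The tally above leaves it out. Visits after recurrence are not a loss either, since a sound analysis may also set them aside.

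**The feeding-tube analysis is weak support.** Section 9.3.2.5 says "The prevalence of feeding tube use will be described at each time point as outlined in section 5.4" and states no exclusion for recurrence. A reader might infer that two analyses at the same visits use conflicting populations. That sentence names no analysis set, so its silence does not show this.

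**The exclusion is openly pre-specified.** True, and a one-line objective need not state analysis populations. But pre-specifying the rule does not stop the early estimates from depending on later outcome.

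**Conclusion.** The point holds for the literal text. Section 9.3.2.4 removes whole patients for an event after baseline, with no time limit, at a cost of 1, 2 or 3 valid change values per excluded patient per instrument. At the section 1.1 rates with constant hazard, that is about 1.0 to 1.5 patients of 20 and 2.2 to 3.2 of 80 values. The early estimates then describe only patients who later stay recurrence-free.

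A reader might infer that quality of life will be materially overstated. The documents do not support that. They give no scores for patients who later recur, so both direction and size of any bias are assumptions, and every scenario shown stays under the 10-point MDADI difference. The MTD, the DLT decisions and the stopping rules do not use this analysis. The change is worth making because the defect is plain and the remedy is cheap, not because the distortion is large.

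**What to change.** Replace the exclusion sentence in section 9.3.2.4 with:

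> For patients with disease recurrence (LRR or DM per section 6.1.1, with residual disease at 12-14 weeks classified as in section 5.3), PRO scores from the assessment at which recurrence was first detected onward are excluded; all earlier scores are analysed. A sensitivity analysis adds the post-recurrence scores collected, and the number of scores at each visit is reported.

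The cut-off is the detecting assessment rather than a progression date because section 6.1.1 gives a dating rule only for distant metastasis without biopsy and none for locoregional recurrence. If the biopsy date were used, the form from the visit that raised the suspicion could count as pre-recurrence. The text leaves the rest of the analysis population as it is, so the replacement provision in section 4.8 is untouched.

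**Cost.** The main analysis needs no new visits or forms, because the earlier scores are already scheduled, and GEE can use patients with different numbers of visits. The downsides are possibly slightly less favourable means, a patient set that shrinks across visits, a 12-month estimate that still describes recurrence-free patients, and one extra analysis that may rest on few post-recurrence forms.

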4.5.1 Subject Withdrawal

In the event a subject chooses to withdraw from the study, document if the is withdrawing from treatment only (and willing to be included in follow-up data collection), or if they are withdrawing from all study participation. For subject safety, the subject should be encouraged to return for a follow-up visit per the Time and Events Table in section 5.4.

Notify the Principal Investigator/Sponsor-Investigator and document the reason for withdrawal from study and the date of discontinuation.

4.6 **Duration of Follow Up**

Patients will be followed for 1 year from the completion of treatment according to the Time and Events table in section 5.4.

4.7 **Removal of Subjects from Protocol Therapy**

Subjects will be removed from therapy when any of the criteria listed in section 5.5 apply. Notify the Principal Investigator (or the co-Investigators if not available) and document the reason for treatment discontinuation and the date of discontinuation. The subject should be followed-up per protocol.

4.8 **Subject Replacement**

Subjects may be replaced in the study if they do not complete RT for reasons not related to toxicities associated with treatment. Because inadequate receipt of treatment may lead to a spuriously high rate of recurrence and/or inaccurate assessment of treatment side effects, these patients may be replaced. Patient replacement must be verified through review of the case by the Principal Investigator (or the co-Investigators if Principal Investigator is not available).

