7.5 Stopping Rules

The primary hypothesis of the phase 1 study is that de-intensified HFRT is safe and tolerable. The trial will terminate during the rolling 6 dose escalation phase if it has reached level -1 and 2 patients experience dose limiting toxicity (DLT) at this dose level.

The secondary hypothesis is that the crude 1-year LRC rate is at least 85% (based on historical controls). In other words, for the target of 20 evaluable patients at 1 year, up to 3

patients can have a LRR and satisfy the pre-specified hypothesis. Thus, if a 4th patient enrolled on the trial experiences LRR within 1 year of completing the study treatment, the trial will be terminated for futility.

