9.2 Sample Size and Accrual

We anticipate 3-6 patients in each cohort with a maximum of 12 total patients (e.g. 6 in level 0, 6 in level 1 or -1) during the Rolling 6 dose escalation phase.

During the dose expansion phase, patients will be accrued until a total sample size of 24 is reached to ensure at least 20 evaluable patients at 1 year assuming an attrition rate of 15%. We anticipate accruing 3 patients per month for a total accrual period of approximately 3 years accounting for time to reach the primary endpoint at 3 months prior to enrolling on to the next cohort.

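### QOL change is to be analysed by GEE with about 20–24 patients and no stated small-sample method; run with the usual defaults, nominal 95% intervals at each visit would cover about 93%

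*Combined protocol and SAP*

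**What the plan says.** Section 9.3.2.4 gives the QOL analysis in a few lines. Scores are numeric at each visit, "Patients with disease recurrence will be excluded", and then: "The changes in these outcomes from baseline to the subsequent time points will be analyzed using generalized estimating equations". It does not name a working correlation, a variance estimator, a reference distribution, a confidence level or a small-sample adjustment.

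The schedule in section 9.1.3 is "MDADI, UW-QOL, and EQ-5D-5L scores at baseline, 1, 3, 6, and 12 months after treatment". That gives four post-baseline visits, and so four mean changes per score.

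On numbers, section 9.2 says "patients will be accrued until a total sample size of 24 is reached to ensure at least 20 evaluable patients at 1 year", allowing for 15% attrition. Section 4.8 permits replacement of some patients who do not complete radiotherapy, so the number treated could slightly exceed 24.

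**The concern.** GEE inference in its usual form uses the robust (sandwich) variance with normal or chi-square reference values. Both are large-sample approximations in the number of clusters, and here the clusters are the patients. With 20 to 24 of them the sandwich variance is biased slightly low and the normal reference is too narrow. Both errors act in the same direction, towards intervals that are too short and p-values that are too small.

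The same shortfall would recur at each of four visits for MDADI, UW-QOL and EQ-5D-5L. Patient-reported QOL is a stated secondary objective (section 2.2.3), and section 6.3.2 gives a 10-point MDADI difference as clinically meaningful. Judging a mean change against that value calls for intervals with their stated coverage.

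**Working it through.** **Inputs.** From the documents: 24 patients enrolled, 15% attrition and at least 20 evaluable (section 9.2), and four post-baseline visits (section 9.1.3). Assumed, because the documents are silent: two-sided alpha 0.05, visit as a factor, approximately normal changes, the uncorrected sandwich and z/chi-square references.

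**The plan's own figure.** 20/0.85 = 23.5, rounded up to 24; 24 × 0.85 = 20.4. The stated sample size reproduces.

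**Coverage at one visit.** With visit as a factor and complete data, the sandwich variance is the sample variance of the changes with divisor n instead of n − 1. The standard error is therefore s·√((n−1)/n)/√n, and the type I error is P(|t with n−1 df| > 1.96·√((n−1)/n)).

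- n = 24: √(23/24) = 0.979, so the SE is 2.1% too small. The effective cut-off is 1.919. Error is 6.8%, coverage 93.2%.
- n = 20: √(19/20) = 0.975, so the SE is 2.5% too small. The effective cut-off is 1.910. Error is 7.1%, coverage 92.9%.

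**Which part matters.** Per-visit type I error when only one element is repaired:

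| | n = 24 | n = 20 |
|---|---|---|
| Neither repaired | 6.8% | 7.1% |
| Variance only (divisor n − 1, z reference) | 6.2% | 6.5% |
| Reference only (t with n − 1 df, uncorrected SE) | 5.5% | 5.5% |
| Both | 5.0% | 5.0% |

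The normal reference contributes more than the SE bias.

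**Width of a correct interval.** The ratio of t to effective cut-off is 2.069/1.919 = 1.078 at n = 24 and 2.093/1.910 = 1.096 at n = 20, so correct intervals are about 8% and 10% wider.

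**A joint test over four visits, if one were used.** The Wald statistic is distributed as [4n/(n−4)]·F(4, n−4) and would be compared with 9.488.

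- n = 24: P(F(4,20) > 9.488 × 20/96 = 1.977) = 13.7%.
- n = 20: P(F(4,16) > 9.488 × 16/80 = 1.898) = 16.0%.
- With the variance corrected but chi-square kept: 12.4% and 14.3%.

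**Simulation check.** This used 1,500 simulated trials per setting, an exchangeable working correlation and a within-patient correlation of 0.5 (assumed). The setting that matches the plan is 24 enrolled with dropout building to 15% by month 12. Coverage was 92.3–93.2% across the four visits and the joint error was 15.1%. Monte Carlo standard error on coverage is about √(0.93 × 0.07/1500) = 0.7 percentage points, so this agrees with the formula.

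**Check of the repair.** A Mancl–DeRouen variance with t and F references was simulated in a harsher setting than planned: 20 enrolled, then 15% dropout, within-patient correlation 0.6, 3,000 trials. It gave 5.3% per-visit and 4.8% joint error.

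**The case against.** Four points on the other side have force.

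*The uncorrected variance is inferred from silence.* Section 9.3.2.4 names GEE only, and GEE is compatible with every correction proposed here. This stands. The documents do not show that the intervals will be too narrow; they show that nothing prevents it and that common defaults would produce it.

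*The large figure belongs to a test that is not in the plan.* A reader might infer that the QOL analysis carries a 14–16% false-positive rate. The documents do not support that: they define no joint test over visits, no alpha and no QOL hypothesis. The figure that bears on the described analysis is about 93% coverage per visit.

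*The effective number might be put too low.* The 20 in section 9.2 is already net of attrition, so taking a further 15% off it counts attrition twice. The recurrence exclusion could lower the number. Section 7.5 tolerates locoregional recurrence "for the target of 20 evaluable patients at 1 year, up to 3" patients, and 20 − 3 = 17 would give 7.5% per-visit error. That is the limit before the futility rule acts, not an expected value.

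*The practical effect is small.* Assume an SD of MDADI change of 15–20 points (not in the documents). The 95% half-width then moves from 5.9–7.8 to 6.3–8.4 points at n = 24, and from 6.4–8.5 to 7.0–9.4 at n = 20. That is about 0.5–0.8 points, against a clinically meaningful difference of 10. No trial decision depends on it.

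These points limit the weight of the concern but do not remove it. The shortfall always runs in the same direction, and one sentence prevents it.

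**Conclusion.** The concern holds as a gap in specification with a modest, calculable consequence. With 20–24 patients as clusters, GEE run with the uncorrected sandwich and normal reference values gives about 93% coverage for nominal 95% intervals at each visit (type I error 6.8–7.1%). The main cause is the normal reference; a 2.1–2.5% downward bias in the standard error adds to it. The 14–16% joint error is conditional on a test that the plan does not call for.

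The figures assume visit as a factor, roughly normal changes and alpha 0.05. The closed forms assume complete data; the simulation with planned dropout gave similar results.

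A reader might also conclude that GEE is the wrong method and should give way to a mixed model for repeated measures. That does not follow. GEE with an appropriate variance and reference performs close to nominal here. No operating characteristics were calculated for a mixed model in this setting, and the UW-QOL items in Appendix C have only three to five ordered levels, so a normal-theory model with about 20 patients is not clearly better.

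The effect is confined to secondary QOL inference. The MTD rests on DLTs (section 9.1.1) and the stopping rules on DLTs and locoregional recurrence (section 7.5).

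**What to change.** Keep GEE and add a sentence to section 9.3.2.4 stating that:

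- visit enters as a factor;
- the variance is a bias-corrected sandwich (Kauermann–Carroll or Mancl–DeRouen);
- intervals and tests at each visit use t reference values based on the number of patients, and any joint test over visits uses an F reference with Hotelling-type scaling, (n−4)/[4(n−1)] times the Wald statistic on F(4, n−4);
- mean change with a 95% confidence interval is reported at each visit.

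Correcting the variance while keeping z or chi-square references is not enough, as the working shows.

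The cost is one sentence and standard software, with no new data or procedures. Intervals become about 8% wider at 24 patients and 10% wider at 20. With complete data the Kauermann–Carroll form restores the n − 1 divisor exactly. Mancl–DeRouen goes slightly further, by a factor √(n/(n−1)) in the SE: √(24/23) = 1.02 and √(20/19) = 1.03, so a further 2–3% of width. One of the two should be named before the QOL data are analysed.
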